4.4 Interim Analyses and Data Monitoring

A formal interim analysis is not planned. A DMC will be applied to this study. Periodic data review by a DMC will be performed to monitor safety. An external statistical analysis center will provide results to the DMC.

4.5 Data Rules

Generally, for each date stored in database a set of organizational variables will be derived in order to describe the temporal context of that date in the specific study: Phase of treatment (pre, during or post study treatment), day relative to the start of study treatment, day relative to the end of study treatment will be provided.

4.5.1 Baseline and Change from Baseline

For efficacy endpoints, the efficacy baseline is defined as the last available value prior to or on the date of randomization. In case that there is no available value prior to randomization, the value before the first study medication intake will be used. For AVIVO / HealthPatch

Statistical Analysis Plan

data, baseline is defined as the values recorded during run-in (Week -1). Safety baseline is defined as the last available value before the first study medication intake. If values are missing at the baseline (visit 2, week 0), data recorded at run-in (Visit 1) will be considered as safety baseline value. If run-in record is also missing, the baseline value will be left as missing.

Change from baseline for vital signs or laboratory parameters will in general be displayed as the difference to baseline defined as:

$$\text{Change} = \text{Post baseline value} - \text{baseline value}.$$

In addition, for some parameters the relative change will be defined as

$$\text{Relative change} = 100\% * [(\text{post baseline value} - \text{baseline value}) / \text{baseline value}].$$

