6.2.2 Secondary efficacy variables and analyses

6.2.2.1 Secondary efficacy variables

Secondary efficacy variables across different domains are:

- AVIVO Activity intensity (weekly average; in %) reported values and absolute change from baseline at 20 weeks
- NT-proBNP (pg/mL), measured values (log transformed) and absolute / relative change from baseline at 20 weeks to assess elevated filling pressures
- High sensitivity troponin T (hs-TNT; ng/L), measured values (log transformed) and absolute / relative change from baseline at 20 weeks as a biomarker of myocardial injury
- Three scores from KCCQ, Physical Limitation, Overall Summary Score and Total Symptom Score (Appendix 9.3), derived values by visit and absolute change from baseline

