6.2.3 Exploratory efficacy variables and analyses

Exploratory efficacy variables include:

- Echocardiographic parameters, as described in Section 9.4.3 of Clinical Study Protocol, measured values and absolute / relative change from baseline at 20 weeks
- Mandatory biomarkers, as described in Section 9.4.4 of Clinical Study Protocol, measured values and absolute / relative change from baseline at 20 weeks, including UACR, cystatin-C, NGAL for the evaluation of kidney function
- Time from randomization to CV mortality, HF hospitalization and urgent visits for HF as clinical outcomes (both separate and composite outcomes)
- Time from randomization to all-cause mortality, non-fatal myocardial infarction, non-fatal stroke
- EQ-5D-5L QoL, as described in Section 9.4.6.2 of Clinical Study Protocol, measured values and absolute / relative change from baseline
- KCCQ (Appendix 9.3; excluding symptom stability domain and self-efficacy domain), measured values, absolute change and relative change from baseline
- Change in NYHA class
- Absolute change in score on Borg CR 10 Scale

Time to adjudicated clinical outcome events since randomization (both separate and composite outcomes) will be described by means of Kaplan-Meier estimates by visit in FAS. The subjects who do not have the corresponding clinical outcomes until week 26 (planned Visit 9, upper time limit, i.e. $182+7=189$ days) will be considered as right-censored at the minimum of date of last visit, date of Visit 9, and date of death (in case death is non CV death). KM estimates will be presented by individual treatment groups and by all neladenoson groups pooled as well as 5 mg and 10 mg doses pooled as low dose, 20 mg, 30 mg, 40 mg doses pooled as high dose versus placebo.

Additionally time to adjudicated on-treatment clinical outcome events since randomization (using both separate and composite outcomes) will also be described by means KM estimates

Statistical Analysis Plan

by visit. The subjects who don't have the corresponding clinical outcomes 6 weeks after last dose will be considered right censored at minimum of date of last visit, 6 weeks after last dose and date of death (in case death is non CV death). KM estimates will be presented by individual treatment groups and by all neladenoson groups pooled as well as 5 mg and 10 mg doses pooled as low dose, 20 mg, 30 mg, 40 mg doses pooled as high dose versus placebo.

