6.6 Biomarker analyses

Biomarker data will be described by treatment group by the following summary statistics: arithmetic mean, standard deviation, median, quantiles, minimum, and maximum.

Box plots and line plots of means of biomarkers over visits, by treatment group will be provided.

Additional analyses of safety and efficacy biomarkers and their results will be provided in a separate report.

7. Document history and changes in the planned statistical analysis

List major milestones of the SAP development including the dates they have been reached, e.g.:

- Approval of the SAP, dated 15 DEC 2017.
- Approval of the SAP version 2, dated 15 JUN 2018.

8. References

3. R Core Team (2017). R: A language and environment for statistical computing. R Foundation for Statistical Computing, Vienna, Austria. URL <https://www.R-project.org/>.

Statistical Analysis Plan

4. Bjoern Bornkamp, Jose Pinheiro and Frank Bretz (2016). DoseFinding: Planning and Analyzing Dose Finding Experiments. R package version 0.9-15. <https://CRAN.R-project.org/package=DoseFinding>.
6. Rubin DB. Multiple imputation for nonresponse in surveys. New York: Wiley; 1987.
7. The Kansas City Cardiomyopathy Questionnaire Scoring Instructions (2000-2003), John Spertus MD MPH [<http://cvoutcomes.org/> (6th September 2013)].
8. C. Patrick G, et al. Development and Evaluation of the Kansas City Cardiomyopathy Questionnaire: A New Health Status Measure for Heart Failure, Journal of the American College of Cardiology, 2000; 35(5):1245-55.

9. Appendices

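### For NT-proBNP and hs-TNT, relative change is a plain percent change on an unstated scale, and its arithmetic mean misstates the within-arm change

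*SAP*

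**What the plan says.** SAP 4.5.1 introduces relative change with "In addition, for some parameters the relative change will be defined as" and then gives the formula "Relative change} = 100\% * [(\text{post baseline value} - \text{baseline value}) / \text{baseline value". It does not list the parameters concerned or say on which scale the values enter.

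SAP 6.2.2.1 lists the two biomarkers among the secondary efficacy variables: "NT-proBNP (pg/mL), measured values (log transformed) and absolute / relative change from baseline at 20 weeks to assess elevated filling pressures", and for hs-TNT "High sensitivity troponin T (hs-TNT; ng/L), measured values (log transformed) and absolute / relative change from baseline at 20 weeks". Protocol 10.3.1.2 is worded in the same way.

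SAP 6.2.2.2 sends the secondary variables through MCP-Mod without saying which of the listed forms (log value, absolute change, relative change) is tested. Its worst-value imputation, and the penalty in SAP 6.2.1.4.2, are both written for the log-transformed values of these two biomarkers.

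For reporting, SAP 6.6 states: "Biomarker data will be described by treatment group by the following summary statistics: arithmetic mean, standard deviation, median, quantiles, minimum, and maximum". SAP 4.1 sets a similar default for all metric data. Neither document names a geometric mean, a ratio to baseline or a back-transformation.

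SAP 6.2.3 also lists relative change for the mandatory biomarkers, "measured values and absolute / relative change from baseline at 20 weeks, including UACR, cystatin-C, NGAL for the evaluation of kidney function", with no log transformation.

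**The concern.** Choosing a log transformation accepts that changes in these biomarkers are multiplicative. The natural summary of relative change is then a geometric mean ratio. An arithmetic mean of percent changes weights a doubling (+100%) twice as heavily as a halving (−50%), so it drifts upward even when the net change is nil. If the formula were applied to logged values instead, the result would have no clear meaning.

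The drift has an unwelcome direction. SAP 6.2.2.2 treats a rise in these biomarkers as the worst outcome, so the reported mean makes a real fall look smaller. Protocol 4 and 10.3.2.3 bring secondary variables into the totality of evidence for the phase III decision and the assessment of drug effect across doses. A within-arm percent change that does not agree with the log-scale test would therefore be read by people making that decision.

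**Working it through.** The documents give no figure on this point, so there is nothing to reproduce.

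**Inputs**
- Formula: SAP 4.5.1. Variables: SAP 6.2.2.1. Summary statistics: SAP 6.6.
- Group sizes of 36 (an active arm) and 54 (placebo): Protocol 10.4.
- SD of the natural-log change, s: not in the documents; assumed range 0.3 to 0.8.

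**Step 1: percent change on raw values.** Let r = week 20 / baseline, with ln r normal, mean ln g and SD s. Then the expected mean percent change is 100 × (g × exp(s²/2) − 1). The median percent change and the change in geometric mean are both 100 × (g − 1).

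| s (assumed) | Mean % change, no true change (g = 1) | Mean % change, true 20% fall (g = 0.8) |
|---|---|---|
| 0.3 | +4.6% | −16.3% |
| 0.4 | +8.3% | −13.3% |
| 0.5 | +13.3% | −9.3% |
| 0.6 | +19.7% | −4.2% |
| 0.7 | +27.8% | +2.2% |
| 0.8 | +37.7% | +10.2% |

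Example: at s = 0.6, exp(0.18) − 1 = 0.197. The geometric mean ratio gives 0% in every row of the second column and −20% in every row of the third.

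The direction does not depend on normality. If baseline and week 20 are exchangeable, E[r] = E[(r + 1/r)/2], which is at least 1. With one doubling and one halving, the mean is (100 − 50)/2 = +25%.

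**Step 2: percent change on log values.** A doubling then reads 100 × ln 2 / ln(baseline).
- NT-proBNP in pg/mL: +12.2% from 300 and +8.7% from 3000.
- hs-TNT in ng/L: +43.1% from 5 and +17.7% from 50.
- Unit: a halving of NT-proBNP from 900 pg/mL reads −ln 2 / ln 900 = −10.2%. The same halving in ng/mL reads −ln 2 / ln 0.9 = +658%.

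Both the size and the sign therefore depend on the unit.

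**Step 3: comparison between arms.** Two-group t-tests were simulated with 36 against 54 patients, one-sided 5%, equal s and 20,000 replicates per setting.
- No effect: the mean between-arm difference in percent change was −0.06 points (s = 0.5) and −0.12 points (s = 0.7). One-sided error was 0.047 and 0.046, against 0.049 for log change at both.
- True 25% fall: power was 0.84 with log change and 0.79 with percent change at s = 0.5, and 0.60 and 0.51 at s = 0.7.

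**The case against.** The case for leaving the plan alone is substantial, and most of it stands.

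- **Robust summaries are planned.** SAP 6.6 includes the median and quantiles ("arithmetic mean, standard deviation, median, quantiles, minimum, and maximum") and box plots. On raw values the median percent change is zero when the median log change is zero, so the upward shift does not touch it. This stands.
- **The test is probably already on the log scale.** The imputation and penalty rules are written for log-transformed NT-proBNP and hs-TNT. The arm mean of a log difference is the log of the geometric mean ratio, so the better figure is one exponentiation away. This stands as an inference, but the SAP never states it.
- **The log-scale reading is the less natural one.** In SAP 6.2.2.1 the bracketed log transformation follows the measured values, not the relative change. The figures in step 2 apply only if a programmer reads it the other way. This stands; the remedy is to state the scale.
- **More biomarker analyses may exist.** SAP 6.6 refers to a separate report, so a geometric mean ratio may appear there. That does not settle how the relative change named in this SAP is summarised.

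A reader might also infer three stronger things that the documents do not support:
- **A false dose-response.** With equal variability the shift is common to all arms, and step 3 shows no inflation of error. Nothing in the documents points to unequal variability.
- **Mean plots rising in every arm.** The line plots in SAP 6.6 show biomarker levels, not percent changes. If a biomarker has the same distribution at baseline and week 20, its mean is the same and the plot is flat. Even for percent change, a rise is expected only when there is no change or a fall small relative to s.
- **The same defect in UACR, NGAL, cystatin C or free fatty acids.** The documents give no distribution for them and do not log-transform them, so their skewness cannot be assumed here.

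**Conclusion.** The point holds for NT-proBNP and hs-TNT, and it is minor. Their relative change has no stated scale, and the planned arithmetic mean of a percent change is a biased description of a multiplicative change.

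On raw values the expected reading with no true change is +8%, +20% or +38% for s = 0.4, 0.6 or 0.8. The size rests on these assumed SDs and on a normal log change. The upward direction with no change rests only on exchangeability.

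The consequence is a misleading within-arm figure. If percent change rather than log change is the tested variable, there is also a power loss of about 5 points at s = 0.5 and 9 points at s = 0.7 for a true 25% fall. The dose-response test keeps its error rate when variability is equal, the medians on raw values are unaffected, and the level plots are not shown to be affected.

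**What to change.** 1. In SAP 6.2.2, state that MCP-Mod for NT-proBNP and hs-TNT uses ln(week 20) − ln(baseline). This matches the scale of the imputation rules in 6.2.1.4.2 and 6.2.2.2.
2. For these two biomarkers, report relative change as the geometric mean ratio to baseline, exp(mean of ln(week 20) − ln(baseline)), with a 90% CI, the default level in Protocol 10.3.2. It can replace the arithmetic mean percent change. Alternatively it can stand beside it, which keeps the variable listed in Protocol 10.3.1.2; the percent change should then be stated to be on raw values.
3. Apply the same summary to any other mandatory biomarker found to be right-skewed at the blinded data review (SAP 4.6).

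The cost is a few lines of SAP text and some extra table shells. No new data are needed.

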4.5.2 Repeated Measurements

If more than one assessment occurred at any post-baseline visit (repeated measures at same visit), the last valid (non-missing) value will be used in the summaries.

At all post-randomization visits and if not stated otherwise, only the values at scheduled time points will be used for analysis, although unscheduled results will be included in tables reporting any abnormalities, e.g. incidences of high laboratory abnormalities.

For the derived visit “Any time post baseline” this will include any measurement after initiation of study drug, including unscheduled assessments.

4.5.3 Laboratory Data Handling

The data of hematology, clinical chemistry, and coagulation will be provided by central laboratories. Additional re-tests for liver monitoring will be done locally.

For values which are below the lower limit of quantification (LLOQ), half the value of the LLOQ will be used for analysis. Differences between two values of below the LLOQ will be assigned values of 0.

In case of measurements above the upper limit of quantification (ULOQ), the following rules will be applied:

- The ULOQ will be used for calculations.
- Corresponding tables and figures will get a footnote indicating that “Values above the upper limit of quantification of ULOQ were replaced by ULOQ.”
- Tables displaying maximum values will show up “>ULOQ” as maximum.

Unscheduled laboratory data will be listed and included in the summary tables.

4.5.4 Subgroup Analyses

In order to assess the homogeneity of the dose response across the most important prognostic and predictive factors, subgroup analyses will be performed.

‘Key’ subgroups include:

- LVEF (%) at baseline: <55 vs. ≥ 55

Statistical Analysis Plan

Protocol No.: < BAY 1067197/17582>

Page: 13 of 38

- NT-proBNP (pg/mL) at baseline: ≤ median vs. > median
- NYHA class at baseline: II vs. III / IV
- Prior β-blocker: yes vs. no

All other exploratory subgroups comprise demographic and baseline characteristics specified in Section 6.1.2.

If the total number of patients in a subgroup category is too small, the respective subgroup category will be either omitted from the analysis or combined with other categories, if a logical combination to another subgroup category is possible.

4.6 Blind Review

The results of the final data assessment will be documented in the final list of important deviations, validity findings and assignment to analysis set(s). Any changes to the statistical analysis prompted by the results of the review of study data will be documented in an amendment and, if applicable, in a supplement to this SAP.

5. Analysis Sets

Documentation of protocol deviations and assignment of patients to analysis sets will be performed according to the sponsor's applicable Standard Operating Procedures and / or Operation Instructions.

The primary efficacy variables will be analyzed using the per-protocol set (PPS) and the full analysis set (FAS) for sensitivity analyses.

5.1 Assignment of analysis sets

Final decisions regarding the assignment of patients to analysis sets will be made during the review of study data and documented in the final list of important deviations, validity findings and assignment to analysis set(s) (see Section 4.6).

Data for all patients who signed informed consent but were not randomized will not be included in any statistical analyses except standard disposition tables and listings provided in the clinical study report (Screening failures and discontinued patients).

The statistical analysis sets are defined as follows:

Full analysis set (FAS)

The FAS population consists of all randomized unique patients. According to the ICH E9 guideline, this analysis set is as complete as possible and as close as possible to the intent-to-treat (ITT) ideal. Patients will be analyzed as randomized. The FAS will be used to display baseline characteristics and to display efficacy analyses. Sensitivity analyses of efficacy variables are based on the FAS population. For the analyses conducted in FAS, patients will be analyzed as randomized per IxRs.

Safety analysis set (SAF)

Statistical Analysis Plan

Protocol No.: < BAY 1067197/17582>

Page: 14 of 38

The SAF population consists of all randomized patients who received at least one dose of study medication after randomization. The SAF will be used to display baseline characteristics and to display safety analyses. For analyses conducted in SAF, patients will be analyzed as treated.

Per-protocol set (PPS)

The PPS population consists of all FAS population patients without validity findings. Validity findings may include adherence and compliance issues and the violation of inclusion / exclusion criteria affecting efficacy evaluation. A list of potential validity findings will be provided in a separate document which will be finalized before database lock. The detailed definitions and the assignment of patients to this analysis set will be based on the blind review meeting. Patients will be analyzed as treated. The PPS will be used to display efficacy analyses. If the 6MWD of this subject is measured after first dose of study medication but within a specified time frame this subject will not be excluded from PPS.

Pharmacokinetic analysis set (PKS)

The PKS population consists of all patients treated with neladenoson bialanate with at least 1 valid BAY 84-3174 plasma concentration and without protocol deviation that would interfere with the evaluation of the PK data.

6. Statistical Methodology

The formal statistical analyses will be both descriptive and inferential. Summaries will be provided for each of the treatment group. All analyses planned in this SAP will be repeated in Japanese patients only.

6.1 Population characteristics

6.1.1 Disposition of Subjects

The following will be tabulated overall and/or by treatment group:

- Study sample sizes (FAS, PPS, SAF and PKS)
- Study sample sizes by region, country, and site
- Subject disposition
- Number of subjects and primary reasons for screening failures (only overall)
- Number of subjects and primary reasons for premature discontinuation of study medication (by treatment group and overall for FAS and SAF)
- Number of subjects and primary reasons for discontinuation from study (by treatment group and overall for FAS and SAF)

6.1.2 Demographic and Baseline Characteristics

Descriptive summaries of demographics and baseline characteristics will be presented by treatment group and overall for the PPS, FAS and SAF populations. Comparability of the

Statistical Analysis Plan

treatment groups with respect to demographics and baseline characteristics will be assessed using the descriptive summaries. Same analyses will also be performed for subjects who prematurely discontinue study participation or intake of study medication.

The following demographic data will be summarized:

- Age at baseline (years)
- Age category: <65, 65-75, >75 years
- Age category (only for the EMA results posting): <65, 65- <85, >=85 years
- Gender (male vs. female)
- Race / ethnicity
- Region
- Height (cm)
- Weight (kg)
- BMI (kg/m²)
- BMI category (≤ 30 vs. >30 kg/m²)
- Tobacco smoking history
- Alcohol consumption history
- Recent caffeine-containing beverage and chocolate consumption history

The following baseline characteristics will be summarized:

- LVEF (%): <55 vs. ≥ 55
- LVEF (%): < 50 vs. ≥ 50
- NT-proBNP (pg/mL): \leq median vs. $>$ median
- NYHA class: II vs. III / IV
- Prior β -blocker: yes vs. no
- Time of CHF diagnosis to randomization (months): ≤ 3 vs. >3
- Time of CHF diagnosis to randomization (months)
- Diabetes Mellitus type 2: yes vs. no
- Atrial fibrillation (AF): yes vs. no
- Arterial Hypertension: yes vs. no
- Nocturia: yes vs. no
- Estimated GFR (mL/min/1.73 m²): ≤ 60 vs. >60
- 6MWD

Statistical Analysis Plan

Protocol No.: < BAY 1067197/17582 >

Page: 16 of 38

- History of coronary artery disease: yes vs. no
- Subject group (LA enlargement or/and LV hypertrophy vs. Elevated filling pressures vs. Combination of structural inclusion criterion and additional hemodynamic inclusion criterion vs. Other) in the 6 months prior to run-in
- Based on centrally evaluated echos during the study (i.e. Week 0):
 - LA enlargement (LA diameter ≥ 3.9 cm, LA volume ≥ 55 mL, LAVI ≥ 29 mL/m², or LAA ≥ 20 cm²)
 - LV hypertrophy (septal or posterior wall thickness ≥ 1.1 cm)

6.1.3 Medical history

Medical history findings will be summarized using medical dictionary for regulatory activities (MedDRA, version refers to the Trial Summary (TS) domain) terms for the FAS population by treatment group.

6.1.4 Prior and Concomitant Medications

All non-study medications taken during the study will be coded using the World Health Organization Drug Dictionary (WHO-DD) and the Anatomical Therapeutic Chemical (ATC) classification system. Coding will include the drug class and preferred drug name.

Non-study medications taken during the study will be categorized as prior medications, concomitant medications during the treatment period, and post treatment medications during the safety follow-up.

Prior medications will be defined as a non-study medication with a stop date prior to the first dose of study treatment.

Concomitant medications will be defined as:

- Non-study medications with a start or stop date on or after the date of the first dose of study treatment;
- Non-study medications that started prior to the first dose of study treatment and are ongoing during the treatment period;
- Non-study medications with partial start dates that indicate that the medication could be concomitant in relation to the date of the first dose of study treatment;
- Non-study medications with completely missing start dates, unless their stop dates confirm otherwise (i.e. the stop date is before the first dose of study treatment).

Post treatment medications are defined as non-study medications taken up to 6 weeks after the last study medication intake.

All concomitant medications will be listed, including verbatim descriptions and coded terms, and flags for prior medications. Prior, concomitant, and post treatment medications will be summarized using frequencies of patients reporting each drug category and preferred drug name. Relevant concomitant medications to treat comorbidities, i.e. ACEIs, ARBs, beta blockers, MRAs, digitalis glycosides, loop and thiazide diuretics, Potassium sparing agents

Statistical Analysis Plan

Protocol No.: < BAY 1067197/17582>

Page: 17 of 38

(excluding MRAs), Statins, anticoagulants, antiplatelets, GLP-1 antagonists, insulins, and SGLT-2 inhibitors will be summarized using frequencies of subjects reporting each preferred drug name at baseline and post-baseline.

For each subject, multiple records of the same concomitant medication will be counted once within a drug class and preferred name.

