4.3 Handling of Missing Data

Generally, missing data will be handled as such, i.e., no imputation of missing data will be performed. An exception is the analysis of the primary and secondary efficacy variables, and the timing of events relative to other events.

All missing or partial data will be presented in the patient data listing as they are recorded in the eCRF.

A number of descriptive analyses will be performed to better understand missing data patterns. The frequency, proportion and the reasons for premature discontinuation of both the study and study treatment will be reported. Kaplan-Meier plots for “time to end of study treatment (calculated as days from first dose to the earliest date of stop medication, including premature stop of study medication and death, for the calculation all the subjects will be considered to have an event, i.e. stop of study medication)” and “time to end of study” (calculated from randomization to the earliest date of visit 9, death, and the last visit if subject drops off from study prematurely, for the calculation all the subjects will be considered to have an event, i.e. stop of study) will be provided, by treatment group and overall.

The number of patients who prematurely discontinue study participation or intake of study medication and the corresponding reasons will be summarized with respect to the key subgroups (see Section 4.5.4). If the proportion of patients who withdraw across the dose groups is not fairly balanced, the impact on the primary variables will be further explored. To further explore the missingness pattern with regards to the “missing at random” assumption, the mean of the baseline values of the efficacy variable will be summarized for patients with and without post-baseline observations, by treatment group and overall.

For the analysis of the primary and secondary variables, it cannot necessarily be assumed that data are missing at random. As the choice of primary analysis will be based on assumptions that cannot be verified, the robustness of the results of the primary analysis will be investigated through appropriate sensitivity analyses making different assumptions, in accordance with the EMA “Guideline on missing data in confirmatory clinical trials”. Detail missing data handling are specified in Section 6.2.1.4.

When appropriate, the following rules will be implemented so as not to exclude subjects from statistical analyses due to missing or incomplete data:

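### Does the SAP's definition of prior medication undermine the key subgroup of prior β-blocker users?

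*SAP*

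**What the plan says.** Protocol 10.3.2.1 and SAP 4.5.4 both list "Prior β-blocker: yes vs. no" among four key subgroups. The protocol leaves further subgroup detail to the SAP, and the SAP repeats the label without a reference date, time window or data source. SAP 6.1.2 lists the item again, under the lead-in "The following baseline characteristics will be summarized".

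SAP 6.1.4 deals with medication records: "Non-study medications taken during the study will be categorized as prior medications, concomitant medications during the treatment period" and post-treatment medications. It states: "Prior medications will be defined as a non-study medication with a stop date prior to the first dose of study treatment". One of its definitions of a concomitant medication is "Non-study medications that started prior to the first dose of study treatment and are ongoing during the treatment period". The same section says that a list of drug classes relevant to comorbidities, β-blockers among them, "will be summarized using frequencies of subjects reporting each preferred drug name at baseline and post-baseline".

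For sparse categories, SAP 4.5.4 says that "the respective subgroup category will be either omitted from the analysis or combined with other categories", the latter where a logical combination exists.

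**The concern.** The word *prior* appears in a key subgroup label, and the only definition of prior medication in the SAP requires that the drug had been stopped. A programmer who carried that definition across would put a patient on stable β-blocker therapy throughout the trial in the no category, beside patients never exposed. SAP 6.1.4 also plans a flag for prior medications in the listings, so a variable with this meaning will exist.

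The subgroup is used in several places. SAP 6.4.2 repeats the dose-response test and the pairwise comparisons of 6-minute walking distance within key subgroups, SAP 6.4.3 summarises adverse events and ECG abnormalities by them, and SAP 4.3 does the same for premature discontinuations. Protocol 3.4 raises a theoretical concern that bradycardia and higher-degree AV block might be worse with concomitant β-blockers. A split that mixes continuing users with never-users could not inform that question.

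**Working it through.** The plan states no figure to reproduce on this point. The check compares the possible readings with the text and then sizes the difference.

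**Three readings of the label**

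- A: a β-blocker stopped before first dose (SAP 6.1.4 carried over).
- B: a β-blocker ongoing at baseline.
- C: any β-blocker use before first dose.

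Never-users are *no* under all three. B and C differ only by patients who had stopped, and the documents give no count of these.

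**Which reading the text supports**

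1. SAP 6.1.4 classifies medication records for coding, listing and frequency tables. Neither SAP 4.5.4 nor SAP 6.1.2 refers to it for the subgroup.
2. SAP 6.1.2 treats the item as a baseline characteristic, next to baseline ejection fraction, NT-proBNP and NYHA class.
3. SAP 6.1.4 itself tabulates β-blockers at baseline, so baseline use is already to be derived.
4. Protocol 10.3.2.1 has an exploratory subgroup on whether the prior β-blocker was at the maximum tolerated dose. That describes current background therapy, not a drug already stopped.
5. The safety interest in protocol 3.4 is in concomitant use.

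All five points are against A. Points 2 to 5 favour B.

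**Size of the gap between A and B**

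Inputs: expected per-protocol set N = 0.75 × 288 = 216 (protocol 10.4); β-blocker use u of up to 0.80 (protocol 3.3, a background statement about patients with this disease, so a ceiling). As assumptions to show the range: u down to 0.50, and a share s of 0 to 0.10 of users with a β-blocker record that ended before first dose, for example after a product switch.

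Under B: yes = N·u and no = N·(1 − u).

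- u = 0.80: 172.8 yes, 43.2 no.
- u = 0.50: 108 yes, 108 no.

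Under A: yes = N·u·s and no = N − N·u·s; share of the no group still made up of users with no ended record = (u − u·s)/(1 − u·s).

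| u | s | yes under A | no under A | users' share of no |
|---|---|---|---|---|
| 0.80 | 0 | 0 | 216 | 0.800 |
| 0.80 | 0.10 | 17.3 | 198.7 | 155.5/198.7 = 0.783 |
| 0.50 | 0 | 0 | 216 | 0.500 |
| 0.50 | 0.10 | 10.8 | 205.2 | 97.2/205.2 = 0.474 |

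So A and B are far apart, and A leaves between 0 and about 17 patients in the yes category over six arms.

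**Whether A could pass unnoticed**

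The run-in lasts one week. Exclusion criterion 2 requires two weeks without initiation or dose modification of cardiovascular drugs, although it does not say that stopping counts as a modification. Both suggest few patients with a β-blocker stopped just before dosing. A yes category of that size, against a baseline table with many β-blocker users, is a conspicuous mismatch. It can be seen without treatment codes, and SAP 4.6 provides for documented changes prompted by the data review.

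**What depends on the subgroup**

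The primary multiple contrast test in SAP 6.2.1.2 has no β-blocker term. The adjusted analysis in SAP 6.2.1.5 uses baseline walking distance, age and gender. Randomization is stratified by atrial fibrillation only (protocol 7.3). Protocol 10.3.2 claims no formal error control beyond the primary analysis of the primary variable, and SAP 6.3 plans no formal tests for safety.

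**The case for a change.** The strongest case for a change is that a prespecified key subgroup should not depend on inference. The protocol promised the detail, the SAP did not supply it, and the one definition that shares the label's key word gives the wrong split. A definition written before unblinding would cost one line and would remove any suspicion that the categories were chosen with results in view. The subgroup also bears on a safety question that the protocol itself raises.

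Part of this stands. The label is undefined, the wording clashes with SAP 6.1.4, and nothing in the text settles B against C. What does not stand is the step from an undefined label to a likely wrong analysis. That step needs an analyst to take a rule for sorting records, apply it to a patient-level baseline factor with no instruction to do so, and then accept a nearly empty category in a population where the protocol expects β-blockers to be common. If that did happen, the small-category rule in SAP 4.5.4 might lead to a dropped subgroup, or the data review to a redefinition. Either would be visible.

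The figure of 173 also needs care. It uses the top of a background range, and it assumes that no continuing user has an earlier β-blocker record that ended before first dose.

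**Conclusion.** No change to the plan is needed. This is a loose label whose meaning the surrounding text makes reasonably clear, namely β-blocker use at baseline. Analysts can be expected to derive it that way and to record the rule in the programming specification.

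The literal alternative would reclassify up to about 173 of 216 per-protocol patients at 80% use, or up to 108 at an assumed 50%. Neither document calls for that alternative, and its result would be hard to overlook. The outputs concerned are subgroup analyses without error control and descriptive summaries. The overall dose-response test, its one-sided 5% error level and the planned 288 patients do not depend on it.

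The conclusion rests on two judgements: that the context is read as above, and that the few patients who stopped a β-blocker shortly before dosing, whose number the documents do not give, are too few to matter to the choice between use at baseline and any earlier use.
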